### **3. Provide a justification for the sample size used in this protocol.**

Include sample size calculations or statistical power estimation. If not applicable, please provide explanation.  
Also include the anticipated accrual rate, the accrual goal for the study, including accrual goals by strata if appropriate, adjustments for drop-outs etc. and study duration.

Answer/Response: This is a pilot study and no power analysis was performed. We anticipate enrollment in 2 years.

### **4. What is your plan for primary variable analysis?**

Include primary outcome(s)/predictor variable(s), statistical methods/models/tests to be employed, or descriptive summaries as appropriate. If not applicable, please provide explanation.

Answer/Response:

Outcomes: the primary outcome of the study will be any allogeneic blood transfusion within the first 24 hours after administration of the FC or cryoprecipitate.

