**2. What are the statistical considerations for the protocol?**

The objectives section and the statistical section should correspond, and any objective for which analysis is unfeasible should be deleted. Also, the estimates and non-statistical assumptions of the statistical section should be supported by discussion in the background section.

The answer to this question should include:

- Study Design/Endpoints
- Recap of study objectives and endpoint definitions. An assessment of how study objectives will be assessed by identifying & defining which endpoints will be used to assess each component of the study objectives.
- The study design should include contingencies for early stopping, interim analyses, stratification factors (If applicable), and any characteristics to be incorporated in analyses.
- The power/precision of the study to address the major study endpoint(s), the assumptions involved in the determination of power/precision.

--If statistical hypothesis testing is included then specify the null and alternative hypotheses, the test statistic, and the type I and II error rates  
--If precision of an estimate, then provide a definition for precision  
--If other, then specify

Answer/Response: Baseline clinical and demographic characteristics, follow-up measures, and clinical outcomes will be compared on an intention-to-treat basis according to the randomized study group assignment. Continuous variables will be compared using the Student *t* test for normally distributed variables or the Mann-Whitney *U* test or Wilcoxon matched-pairs signed-rank test for non-normally distributed variables. Categorical variables will be compared using the Pearson  $\chi^2$  test or Fisher exact test as appropriate. We estimate that 30 patients would be needed (15 in each study arm) to determine that an exposure to 2 additional allogeneic blood products will be statistically significant (C.I. 95%) providing 80% power with a type I error probability  $\alpha = 0.05$  (including 20% dropouts/withdrawals from the study)

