- Need for additional transfusion (PRBC/cell saver/FFP/platelets/cryoprecipitate). Will need to know, if possible, whether transfused from same unit that was already exposed to in the OR or new unit (= new exposure)
- Factor VIIa administration
- re-exploration? (= starting ECMO in the PICU)
- delayed chest closure? (will answer whether went to PICU with chest open)

**2. If this protocol involves study treatment, explain how a subject will be transitioned from study treatment when they have completed their participation in the study.**

**Example:** If the subject will be taking an investigational drug, will they need to be put back on an approved drug when they have completed the study? If yes, explain how this will be accomplished and who will cover the cost. If the subject has a device implanted will it be removed? Again- who will cover the cost of the removal?

**Instructions:** Answer NA if this study does not involve a study treatment.

Answer/Response: There is no transition from study treatment.

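### The primary outcome is worded as a yes/no event but the trial is sized on a difference of 2 products, so the stated 80% power does not apply to the outcome as written and is unsupported even for a count

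*Combined protocol and SAP*

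**What the plan says.** Statistical Considerations, item 4 (primary variable analysis), is a single sentence: "the primary outcome of the study will be any allogeneic blood transfusion within the first 24 hours after administration of the FC or cryoprecipitate". It gives no unit of measurement, summary measure, test or expected rate.

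Item 2 of the same section carries the sample size: "We estimate that 30 patients would be needed (15 in each study arm" are needed "to determine that an exposure to 2 additional allogeneic blood products will be statistically significant", "providing 80% power with a type I error probability" of 0.05. It says that 20% dropout is already included. It gives no SD and no time window for the 2 products. It assigns Pearson chi-square or Fisher's exact test to categorical variables, and the t test or Mann-Whitney U to continuous ones.

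Item 3 describes the study as a pilot for which no power analysis was carried out. Human Participants, item 2, expects 5% screen failure, dropout and withdrawal, which takes 30 to 32 enrolled.

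Study Procedures, item 1, has intraoperative transfusions recorded as units of each product. The postoperative list adds, where possible, "whether transfused from same unit that was already exposed to in the OR or new unit (= new exposure").

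**The concern.** The two statements describe different variables. "any allogeneic blood transfusion within the first 24 hours" is an event that each child has or does not have. "an exposure to 2 additional allogeneic blood products" is a difference in how many products a child receives. A difference of 2 products cannot be converted into two event proportions without further information, and the protocol supplies none. The 80% therefore has no link to the outcome it is meant to support.

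Two things are at stake. First, if the primary analysis follows the text, it is a comparison of two proportions with 15 children per arm, which detects only very large differences. Second, allocation is unblinded and the protocol does not settle whether the primary outcome is an event or a count. The measure and the test could then be chosen after the data are seen.

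**Working it through.** **1. Can the plan's own figure be reproduced?** Inputs from item 2: difference Δ = 2 products, power 80%, α = 0.05, 30 patients including 20% dropout. Two-sided testing is assumed, because sidedness is not stated. The SD is missing, so it can only be back-solved.

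- Evaluable patients: 30 × (1 − 0.20) = 24, or 12 per arm.
- Normal approximation: SD = Δ × √(n/2) / (1.960 + 0.842). With n = 12: 2 × √6 / 2.802 = 1.75.
- Noncentral t, n = 12: SD ≈ 1.67.
- If all 15 per arm are evaluable: 1.96 (normal), 1.89 (t).
- Forward check with SD 1.7: n = 2 × 1.7² × 2.802² / 2² = 11.3, rounded up to 12 per arm. Then 24 / 0.80 = 30.

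So 30 is arithmetically possible for a count with an SD near 1.7, a value that the protocol does not give. Sensitivity to the SD (t test, Δ = 2):

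| SD | Power, 12 per arm | Power, 15 per arm |
|---|---|---|
| 1.67 | 80% | 89% |
| 2.0 | 65% | 75% |
| 2.5 | 47% | 56% |
| 3.0 | 35% | 42% |

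**2. Power if the outcome is yes/no.** Test: two-sided Fisher's exact, one of the tests that item 2 assigns to categorical variables. Power is the sum, over all tables with p ≤ 0.05, of the product of the two binomial probabilities. The event rates are assumptions.

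| Control vs FC | 15 per arm | 12 per arm |
|---|---|---|
| 90% vs 70% | 15% | 10% |
| 90% vs 60% | 33% | 23% |
| 80% vs 50% | 25% | 21% |
| 95% vs 45% | 82% | 69% |

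With 15 per arm, 80% power needs FC to lower the proportion from 95% to about 46%, from 90% to about 37%, or from 80% to about 24%. Over control rates from 50% to 100%, the required fall is about 41 to 56 percentage points.

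**3. What significance would take.** Suppose all 15 control children are transfused.

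- 4 of 15 FC children escape transfusion: p = 2 × C(15,4)/C(30,4) = 2 × 1365/27405 = 0.100.
- 5 of 15 escape: p = 2 × C(15,5)/C(30,5) = 2 × 3003/142506 = 0.042.

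At least a third of the FC arm would have to receive no allogeneic product at all, however many products the others were spared.

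**The case against.** The strongest reply is that *any* means of any type. Item 5 lists individual blood products as secondary outcomes, so item 4 may intend the total across products. The 2-product effect and the unit-level data collection would then fit. This reading is reasonable and cannot be excluded. It does not settle the matter, because item 4 states no total, unit or summary measure, and the 80% would still lack an SD.

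A second reply is that this is a pilot with no power analysis, so power is beside the point. Item 3 says so, but item 2 claims 80% power. One of them has to give way, and a pilot still needs a defined primary outcome.

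Third, the event rates in the tables are not from the protocol. That is correct. The mismatch itself needs no rates, and the low power for falls of 10 to 30 points holds across assumed control rates of 50% to 95% (about 3% to 40% at 15 per arm).

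Three stronger inferences should be resisted:

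- A reader might conclude that the arms separate only if FC almost abolishes transfusion. The figures do not say that: at 95% vs 45%, nearly half of the FC arm is still transfused.
- A reader might take it as established that nearly every child will be transfused, from the bleeding and low-fibrinogen entry criteria and the hemodilution described in the Background. That is plausible, but no rate is given, and the outcome counts only transfusion after the study product.
- A reader might say that a yes/no outcome has no test. Item 4 names none, but item 2's general rule for categorical variables would cover it.

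**Conclusion.** The point holds. The 80% power does not apply to the primary outcome as written, and it is not demonstrated for a count either. Read as yes/no, the trial has about 15% to 33% power for falls of 20 to 30 points from an assumed 90%, and reaches 80% only when the proportion transfused is roughly halved or cut further. Read as a count, 80% power with 12 evaluable per arm requires an SD of about 1.67 that appears nowhere; at an SD of 2.5, power is about 47%.

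The conflict between items 2, 3 and 4 rests on the text alone. The sizes rest on assumed event rates and SDs, two-sided α = 0.05 and, for the count, a t test on data that may well be skewed. Which outcome was intended cannot be determined from the documents, and that is the main reason the wording must be fixed.

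**What to change.** - **Outcome.** Define the primary outcome as the total number of allogeneic units per patient in the 24 hours after administration of the study product, built from the units-per-product data. Exclude the randomised study doses themselves in both arms, including a second one if given. Cryoprecipitate is itself on the transfusion list, so counting study doses would add units to the control arm by design. Say whether cell-saver blood, which is on the same list, is counted.
- **Analysis.** Name one test suited to counts, for example Mann-Whitney U, which item 2 already lists. Report the between-arm difference with a 95% CI.
- **Other measures.** Report any transfusion (yes/no) descriptively. Keep new donor exposures secondary: they are recorded only where possible and only on the postoperative list.
- **Sample size.** State the SD and its source that support 80% power, or withdraw the power claim in line with item 3. Reconcile the 20% dropout in item 2 with the 5% in Human Participants, item 2.

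The cost is small and mostly wording. The instruction to count units should be repeated on the postoperative list, and transfusion times are needed to place units after the study dose. The power statement may become less favourable. If the sponsor prefers the yes/no outcome, it should state the expected rates and recompute the power, or present the result as pilot estimation.

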FC is a lyophilized, nano-filtered and pathogen reduced and inactivated human fibrinogen concentrate with a constant content of 900-1300 mg/vial (final concentration 20g/L). While cryoprecipitate is still in use in North America, it is not available in Europe (except for the UK) due to safety concerns, as it does not undergo pathogen reduction and inactivation. FC has several important potential advantages over cryoprecipitate including: standardized fibrinogen content, higher purity, faster preparation without need for blood bank processing or cross-matching (which also eliminates the risk of human-related transfusion errors), improved safety via pathogen reduction, avoidance of transfusion related acute lung injury (TRALI) and significantly decreased volume of transfusion (which may be particularly important in children with congenital heart diseases as they may be intolerant to excessive volume overload). Yet, cryoprecipitate may be a better hemostatic agent as it also contains factors VIII and XIII, fibronectin, von Willebrand factor and platelet microparticles, all of which are important for normal hemostasis in bleeding patients. Hence it is not known whether FC will provide hemostatic efficacy similar to cryoprecipitate in bleeding pediatric cardiac surgery patients.

Initial studies evaluating the use of FC in cardiac surgery patients reported conflicting results. Surprisingly, several studies failed to report a benefit with the use of FC mainly due to enrollment of patients who did not have low fibrinogen levels. A recent large randomized controlled study in adult cardiac surgery patients, however, demonstrated non-inferiority of FC compared to cryoprecipitate in bleeding cardiac surgery adult patients with low fibrinogen levels (and as a matter of fact FC was found to be superior over cryoprecipitate in regard to several outcome measures). Hence it seems that FC may be a better alternative for fibrinogen supplementation in bleeding cardiac surgery patients compared to cryoprecipitate.

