**INSTRUCTIONS:**

The stratification factors and/or the randomization plan should be identified. If there is no randomization component or important patient characteristics that will be used in treatment allocation or data analysis, a statement to this effect should be included.

Stratification factors: These are pretreatment patient characteristics which could be balanced across treatment arms by design or may be used to determine starting dose or treatment allocation.

If randomization is going to be used, the details of the randomization plan should be described.

The description should include:

- the method and timing of randomization
- the type of randomization scheme that will be used in the study
- whether or not the randomization masked/blinded/if so, then to whom is it masked/blinded
- who has access to the randomization scheme

Answer/Response:

- Once the need for fibrinogen supplementation is confirmed after separation from CPB, patients will be randomized into one of two treatment groups (n=15 in each group):
  1. Cryoprecipitate group (dose: 10 ml/kg; active control group) or
  2. Fibrinogen Concentrate group (dose: 70 mg/kg; intervention group).
- 1:1 randomization unblinded using a computer generated randomization list

► IF YES, who will generate the randomization scheme?

\_\_\_\_\_ Sponsor

\_\_\_\_\_ UVa Statistician.  Insert name Answer/Response:

\_\_\_\_\_ UVa Investigational Drug Service (IDS)

\_\_x\_\_ Other:  Specify Answer/Response: computer generated by the CRC

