**Study Procedures-Biomedical Research**

**1. What will be done in this protocol?**

**INSTRUCTIONS:**

This should include everything that will be done as part of this protocol. Do not repeat information that is included in other sections such as Background or Hypothesis sections.

This section should include an indication of which research interventions if any offer a prospect for direct benefit and which interventions (invasive measurements, collection of blood, tissue, data, surveys, etc.) are being done solely to answer a research question and generate generalizable knowledge. If the interventions done solely for research purposes are associated with greater than minimal risk they need to be justified.

Describe and justify any control and experimental arm and include method, dose, and duration of drug administration. Reference any claim of clinical equipoise if applicable.

If you are obtaining specimens or data, provide information regarding the type of specimen/data, amount of specimen needed and how the specimen/data will be obtained and what analysis will be done with the specimen/data.

Special note for studies with waiver of consent/waiver of documentation of consent:

Include a statement regarding how subjects will be recruited. For other studies this information is captured in Recruitment does not need to be duplicated in this section.

Answer/Response:

The parent/ legal guardian will be consented at a clinic or hospital visit prior to surgery by study staff and will include the Peds Cardiac NP they are familiar with when possible. Subjects will be monitored for 48 hours for the need for fibrinogen supplementation

Once the need for fibrinogen supplementation is confirmed in the OR or PICU, subjects will be randomized into one of two treatment groups (n=15 in each group):

1. Cryoprecipitate group (dose: 10 ml/kg; active control group) or
2. Fibrinogen Concentrate group (dose: 70 mg/kg; intervention group) single dose.

Administration of the study drug is via transfusion.

There will be no placebo group since withholding treatment is neither consistent with standard of care nor acceptable ethically.

No other aspects of care will be modified.

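### The primary 24-hour window starts at dosing rather than at randomisation, so its start may differ by arm and a randomised infant who is never dosed has no defined primary outcome

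*Combined protocol and SAP*

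**What the plan says.** The only definition of the primary outcome is under Statistical Considerations, question 4: "any allogeneic blood transfusion within the first 24 hours after administration of the FC or cryoprecipitate". It does not say whether administration means the start or the end of the infusion. It also does not say which dose is meant, although Study Procedures allows a second assigned dose.

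Randomisation precedes dosing in both places that describe it. Statistical Considerations, question 1, says: "Once the need for fibrinogen supplementation is confirmed after separation from CPB, patients will be randomized into one of two treatment groups". Study Procedures, question 1, says: "Once the need for fibrinogen supplementation is confirmed in the OR or PICU, subjects will be randomized into one of two treatment groups". Question 1 of Statistical Considerations also specifies "1:1 randomization unblinded using a computer generated randomization list".

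The analysis rule, in Statistical Considerations, question 2, is that "clinical outcomes will be compared on an intention-to-treat basis according to the randomized study group assignment".

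The Background lists among the potential advantages of FC its "faster preparation without need for blood bank processing or cross-matching". No preparation or issue time is given for either product. No maximum interval from randomisation to dose is set, and no rule covers a randomised infant who receives no study product.

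**The concern.** Randomisation makes the arms comparable from the moment of allocation. An outcome window that opens later, at a moment the allocated product can itself influence, no longer has that protection in full.

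Here the skipped interval falls while the infant is bleeding, because clinically significant bleeding is an entry criterion. Red cells, platelets or plasma given in that interval are left out of the primary outcome. If one arm waits longer, more of its bleeding period is left out. The protocol gives its own reason to expect unequal waits.

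The second problem needs no assumption about timing. An infant who is randomised but not dosed has no time zero, so the outcome cannot be evaluated, yet intention-to-treat requires that infant to be compared in the assigned arm.

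At stake is whether the primary comparison, with 15 infants planned per arm, is one of randomised groups over the same period.

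**Working it through.** **1. Order of events.** Need confirmed, then randomisation (time 0), then the product is prepared, then dosing (time W), then the 24-hour primary window. The window is W to W + 24 hours, where a window anchored at randomisation would be 0 to 24 hours.

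**2. What the anchor changes, on a count reading.** For one infant, the count from randomisation minus the count from dosing is

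(units given in 0 to W) − (units given in 24 to 24 + W).

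Both windows last 24 hours; the later one is shifted, not shortened. The between-arm bias is the difference in the mean of this quantity between the arms. It is zero if waits and transfusion patterns are the same in both arms. The documents give neither W nor any transfusion rate, so it cannot be calculated.

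**3. What the anchor changes, on a yes/no reading.** The wording can also mean any transfusion against none. An infant transfused only while waiting then becomes event-free. An infant first transfused after hour 24 but before hour 24 + W becomes an event. Each reclassified infant moves an arm's proportion by 1/15 = 6.7 percentage points.

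**4. Undosed infants.** With 0, 1, 2 or 3 undosed infants in an arm of 15, the outcome is defined for 15, 14, 13 or 12, so 0, 6.7, 13.3 or 20% are missing.

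**5. The plan's own figure.** Statistical Considerations, question 2, gives 30 infants (15 per arm) for a difference of 2 products, 80% power, alpha 0.05, including 20% dropout. The dropout step reproduces: 12/(1 − 0.20) = 15. The base number cannot be reproduced because no standard deviation (SD) is stated, and question 3 says no power analysis was done. The SD that would make it work, two-sided with the normal approximation, is

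SD = 2 / [(1.960 + 0.842) × √(2/12)] = 1.75.

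**6. Illustration of sensitivity, not an estimate.** Assumptions: the outcome is a count, 12 infants per arm are evaluable, SD is 1.75, the assigned dose is not counted, and the cryoprecipitate arm loses a net excess of L products per infant. The standard error is 1.75 × √(2/12) = 0.71. A true cryoprecipitate excess of 2 is then observed as 2 − L, and a true difference of 0 as −L.

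| L (assumed) | Observed difference when truth is 2 | Power | Two-sided rejection rate when truth is 0 |
|---|---|---|---|
| 0 | 2.0 | 80% | 5.0% |
| 0.25 | 1.75 | 69% | 6.4% |
| 0.5 | 1.5 | 56% | 10.8% |
| 1.0 | 1.0 | 29% | 28.8% |

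No value of L can be taken from the documents. The table shows only that a net difference well below one product per infant would matter in a trial of this size.

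**7. A possible effect in the other direction.** Question 5 lists cryoprecipitate among the blood products counted as secondary outcomes. If assigned cryoprecipitate also counts in the primary outcome, through an infusion that runs into the window or a second assigned dose, the cryoprecipitate arm gains events by design. That opposes the effect in step 6.

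**The case against.** The strongest defence is that the hypothesis concerns how well the product achieves haemostasis, and a product cannot act before it is given. Starting at dosing is then a natural choice, and counting transfusions given while waiting answers a broader question about the treatment strategy. This is a reason to keep the window from administration as a supporting analysis. It does not make that window suitable as the primary one under intention-to-treat, because it leaves undosed infants without an outcome.

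A second defence is that the units are collected anyway. Study Procedures does collect intraoperative and intensive-care transfusions, so they are not necessarily lost from the data. But intraoperative products are recorded as unit counts, no timing relative to randomisation is specified, and these data do not feed the primary outcome.

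A third is that this is a small pilot. It still names a primary outcome, and question 2 claims 80% power.

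A reader might also infer more than the documents support:

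- **That the clock hides a real advantage of FC.** Faster preparation is listed only as a potential advantage, without times, and step 7 could work in the opposite direction.
- **That the volumes show cryoprecipitate takes longer to give.** FC at 70 mg/kg and 20 g/L (20 mg/mL) is 70/20 = 3.5 mL/kg, against 10 mL/kg for cryoprecipitate, a ratio of 2.9. No infusion rate is given, so a volume ratio is not a time ratio.
- **That more infants will go undosed in the cryoprecipitate arm.** The documents do not say that any are expected, or that ECMO would prevent dosing. They only leave the case without a rule.

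**Conclusion.** The point holds in a limited form. As written, the primary window opens at a post-randomisation event in an unblinded trial, and the protocol itself gives a reason why the delay before that event may differ by arm. The outcome is also undefined for a randomised infant who is not dosed. This is a gap that the intention-to-treat rule cannot close, because the rule says in which arm an infant is compared but supplies no time zero.

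Both conclusions rest on the text alone. Any statement about size needs waiting times and transfusion rates that the documents do not give; the table is conditional on its assumptions. The direction is likewise open until the plan says whether the assigned cryoprecipitate counts.

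**What to change.** Amend the outcome definition in Statistical Considerations, question 4, and the data list in Study Procedures:

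- Define the primary window as 0 to 24 hours from randomisation for every randomised infant, dosed or not.
- Count allogeneic products other than the assigned study dose or doses.
- Record the times of randomisation, of the start and end of the study dose, and of each transfusion.
- Report the randomisation-to-dose interval by arm.
- Keep the window from administration as a sensitivity analysis, stating whether it runs from the start or the end of the first dose.

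The change adds no patients or procedures and alters no clinical care. The cost is some extra data recording. The section on subject compliance says that administration is documented in the electronic record, but the protocol mentions no randomisation time stamp and no transfusion times, so these should be specified prospectively. The statistical price is that some pre-dose transfusions, which the product cannot affect, enter the outcome and add a little noise.
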